#### **2.4.5 Data Management**

The PI will oversee all aspects of data management. With the consultation of the Data Center (DC), the PI and coordinator will develop an operations manual to standardize all procedures and staff training in areas such as patient recruitment, measurement, assessment, and data entry, management, and security.

Data management will follow the policy and procedures of the DC. The data entry system will be created using .NET 2.0, Microsoft Access, or SQL. We will create a tracking database that will be linked to the data entry database that will monitor enrollment, and track follow-up rates and the data entry process, providing up to date status reports. The database will include routine data edit checks for consistency both within and between forms. DC will work closely with investigative team and other study personnel to ensure that protocols are being followed, data integrity and confidentiality are maintained, and that the data contains a minimum amount of missing data. All study files residing in designated network folders will be backed-up daily and archived weekly. The weekly data are stored in a safety deposit off site (> 1 mile off campus). The weekly archived files are maintained for 1 year until the data are erased. All screened study participants will be assigned unique study identifiers that will appear on all data collection instruments, tapes, documents, and files used in the statistical analysis and manuscript preparation. Only authorized team members will have access to personal information needed for tracking and informed consent. Other data quality assurance measures will include detailed documentation of computer operations and data editing procedures and regular meetings with project staff to review any changes in procedure. The DC also has specific data quality measures that will be implemented. These include data verification, built in data validation mechanisms such as logic and out of range data checks, and repeated evaluation of the data collection and entry process.

### **3. HUMAN SUBJECT**

#### **3.1 PARTICIPANT POPULATION**

Potential participants who meet the inclusion criteria, and have none of the exclusion criteria, will be enrolled without restriction as dictated by the study protocols. We will make efforts to enroll participants in this research in a distribution that mirrors the study population of the Pittsburgh area.

#### **3.2 INCLUSION CRITERIA**

- Age  $\geq$ 70 years
- Sedentary (<1 hour/week of volitional exercise activity)
- Clinically stable (euvolemic; baseline HR <100 bpm) and without hospitalization or invasive cardiac procedure for 6 weeks

#### **3.3 EXCLUSION CRITERIA**

- Blood pressure <110 or >160/95 mmHg
- Participant is at greater risk of hypotensive adverse events caused by sodium nitrate following review of past medical history and physical exam.
- Participants with GPD deficiency in whom sodium nitrate might increase the risk of hemolytic crisis.
- Orthopedic or other chronic condition which limits physical activity or exercise testing assessments
- If valve replacement has been performed, patient may not be enrolled for 12 months after this procedure
- Severe peripheral or pulmonary artery disease
- Anemia: Hgb <11.0 ( $\text{\textcircled{M}}$ ), 10.0 ( $\text{\textcircled{F}}$ ) gm/dl
- Participants with diabetes whose HgbA1c >10.0%

- Chronic alcohol (>14 drinks ETOH a week) or drug (any cocaine, methamphetamine, and cannabis ≥4 x week) dependency
- Allergy to lidocaine; Allergy to Red Dye
- Chronic use of oral corticosteroids or other medications that affect muscle function
- Current use of organic nitrates or phosphodiesterase type 5 (PDE5) inhibitors
- Unable to hold warfarin, direct-acting oral anticoagulants (DOACs), non-steroidal anti-inflammatory medications (NSAIDs) or aspirin for 3 days prior to muscle biopsy, or to hold thienopyridine medications for 5 days prior to muscle biopsy. Participants unable or unwilling to hold will follow the modified ASA hold plan
- Any bleeding disorder that would contraindicate biopsy such as history of clinically significant bleeding diathesis (e.g., Hemophilia A or B, Von Willebrand's Disease or congenital Factor VII deficiency)
- Unstable psychiatric diagnosis that would affect adherence and ability to complete the protocol
- Dementia or inability to give informed consent or follow study protocol
- End-stage disease
- Other chronic unstable disease such as active neoplasm, end stage chronic kidney, liver or other organ disease

#### **Relative Exclusions**

- Participants with a non-3T MRI compatible pacemaker, implantable cardiac defibrillator, stent or other identified metal in their body will be excluded from the Magnetic Resonance Spectroscopy study.
- Subject who use PDE5s for erectile dysfunction and are willing to withhold use 24 hours prior and during entire dosing period may be enrolled.

#### **4. IRB APPROVAL AND FDA AMENDMENTS**

The Investigator will obtain, from the University of Pittsburgh Institutional Review Board (IRB), prospective approval of the clinical protocol and corresponding informed consent form(s); modifications to the clinical protocol and corresponding informed consent forms, and advertisements (i.e., directed at potential research participants) for study recruitment.

The only circumstance in which a deviation from the current IRB-approved clinical protocol/consent form(s) may be initiated in the absence of prospective IRB approval is to eliminate an apparent immediate hazard to the research subject(s). In such circumstances, the Investigator will promptly notify the University of Pittsburgh IRB of the deviation. The Investigator should also notify the sponsor of this event.

The University of Pittsburgh IRB operates in compliance with FDA regulations at [21 CFR Parts 50](#) and [21 CFR 56](#), and in conformance with applicable International Conference on Harmonization (ICH) Guidelines on Good Clinical Practice (CGP).

In the event that the University of Pittsburgh IRB requires, as a condition of approval, substantial changes to a clinical protocol submitted under an FDA-accepted IND application, or in the event of the Investigator's decision to modify the previously accepted clinical protocol:

- For Phase 2 and 3 clinical studies: The Sponsor will submit (i.e., in advance of implementing the change) a Protocol Amendment to the IND describing any change to a Phase 2 or Phase 3 protocol that significantly affects the safety of participants, the scope

of the investigation, or the scientific quality of the study. Examples of Phase 2 and 3 clinical protocol changes requiring the submission of a Protocol Amendment include:

- i. Any increase in drug dosage or duration of exposure of individual participants to the investigational drug beyond that described in the current protocol, or any significant increase in the number of participants under study.
- ii. Any significant change in the design of the protocol (such as the addition or deletion of a control group).
- iii. The addition of a new test or procedure that is intended to improve monitoring for, or reduce the risk of, a side effect or adverse event; or the dropping of a test intended to monitor the safety of the investigational drug.

## **5. RECRUITMENT AND INFORMED CONSENT PROCEDURES**

### **5.1 RECRUITMENT METHODS:**

A variety of mechanisms will be used to recruit participants for this protocol

- a. Potential candidates will be identified through screening of inpatients at the UPMC Presbyterian, UPMC Montefiore, UPMC Mercy, and UPMC Shadyside hospitals. Potential candidates will be identified through screening of inpatients' medical records for subjects 70 years and older with past medical history relative to inclusion and exclusion criteria. Recruiter will request bedside nurse to ask patient if it is okay to approach and explain study. Those interested in participating further will be provided the study brochure and study contact information or the option to complete the initial screening in person.
- b. UPMC patients can be referred by their physician and/or cardiologist from the UPMC Cardiology Center, General Cardiology clinic, Benedum Geriatric Center, the Comprehensive Pulmonary Hypertension (PH) Program or other UPMC or community facility. For UPMC Presbyterian/Montefiore-based clinics, we will obtain physician and HRPO approval for screening of subject medical records for identification of eligible candidates. [name] currently already has and will confirm continued approval from UPMC physician groups to screen their patients. He will engage with additional cardiologists and geriatricians for permission to screen from those clinics. Once identified as preliminarily eligible, the study coordinator/staff will reaffirm with the subject's physician on the clinic visit day that recruitment of the subject is medically appropriate. Staff will also request direction from the attending physician as to the timing of speaking to the subject, i.e., before or after the subject has seen the physician for their visit. This will be done on a case-by-case basis. Study staff will speak with candidates at clinic visits or by telephone call to assess interest and review medical history to assess eligibility.

Participants referred from facilities outside the UPMC Epic medical record system will be provided a medical record release for their cardiologist/physician to release needed documents to confirm eligibility.

Participants can also be identified from the inpatient Cardiology service. The study coordinator will follow the same procedure as for outpatients by screening the inpatient service for participants 70 years of age and older. Such participants will need to be followed for 6 weeks of disease stability before enrollment, but recruitment and ascertainment of interest can be initiated, with consideration of medical circumstances in each case. As noted, permission to speak with participant will be obtained from the Cardiology attending.

- c. Research Registries

Two research registries are available to the PI. The HRPO submission will include the request to use the Clinical Translational Science Institute's PittPlusMe Research Registry, which includes a database of over 90,000 individuals who have indicated their interest in participating in research studies. The PittPlusMe initiative includes the use of engaging participants via social media.

Second, the Claude D. Pepper Center has a Research Registry of over 3000 community dwelling participants that are >60 years of age and is also available once HRPO and Pepper Registry approves.

d. Advertisements

An approved study flier and recruitment brochure will be placed in key places and/or be distributed to physician offices, related clinics, or on other occasions/venues that present as an opportunity to recruit (e.g., a PI speaking engagement or a community outreach event to reach minority participants). Potential participants can self-refer by contacting the study staff via a telephone number/email address that is provided on these advertisements. Study staff will utilize the approved phone screening script when responding to interested candidates. With subject permission, they will be screened on the phone to make a preliminary assessment of eligibility. We will obtain permission to access their medical records in the UPMC database or request records from their provider as needed to further document eligibility.

Advertisement, such as on radio, television, or print copy in newspapers, or bus signs may also be utilized depending on recruitment rates.

e. Once participants have been determined to be eligible from medical record review and attending approval, recruitment and enrollment procedures will then follow, including:

- i. Confirmation of eligibility by PI
- ii. Updating participants' cardiologist and confirming management of holding anti-coagulants medication pre-muscle biopsy per protocol, if needed.
- iii. Setting dates for patient visits with subject and staff will also occur prior to screening visit to maintain timeliness of visits per protocol

Scheduling outpatient screening visits (Consent and Visit 1) where study risks and potential benefits, and rights as a research subject will be described in detail, informed consent will be obtained and where final eligibility will be confirmed

## **5.2 INFORMED CONSENT PROCEDURES**

Participants must provide informed consent. The information about this study will be given to the subject in language understandable to them. Either the physician investigator or a non-physician member of the research team will present the study. They will verbally present a general outline of the research plan, including inclusion and exclusion criteria, to the prospective participant. The consent form, outlining the design of the study, will include the risks and benefits of participating, and will be reviewed and the physician investigator and/or non-physician member of the research team will answer any questions. Prospective participants may take as much time as required to make an informed decision. Written informed consent will be obtained from each participant and the physician investigator prior to performing any research study procedures.

## **6. POTENTIAL RISKS AND BENEFITS**

### **6.1 POTENTIAL RISKS**

### 6.1.1 Risk of Experimental Drug Intervention

Nitrite: Numerous studies have evaluated acute, subacute and chronic drinking water exposures of nitrate and nitrite in laboratory animals and drinking water and dietary exposures in humans. Recent studies are available using high doses of nitrite by oral route in the form of beet root juice. Recent studies have evaluated acute exposures of oral preparations of nitrite and nitrate on PK and BP and are characterized below. More extensive human data is available on parenteral sodium nitrite as it is currently available and approved by the FDA for use in the emergency treatment of cyanide poisoning. It is also notable that neutraceutical preparations are currently being sold with levels of nitrite (12.7 mg per tablet) and nitrate (3.9 mg per tablet).

Sodium nitrite has been used commercially as a food preservative, an anti-corrosive agent, a coloring agent, and an anti-anginal agent, with additional uses in laxatives, burn ointments, and liniments. Amyl nitrite has been inhaled or ingested as a euphoric stimulant. Nitrite has also been found as a contaminant in well water. Literature searches generated case reports of nausea, vomiting, abdominal pain, dizziness, headache, flushing, cyanosis, tachypnea, dyspnea, hypotension and death attributed to excess nitrite (high-dose) exposure from these sources as a consequence of methemoglobinemia due to oxidation of heme-iron in oxyhemoglobin. Normal background methemoglobin production is 1-3%. If levels of methemoglobin rise above approximately 30% of total hemoglobin, a subject may appear cyanotic and experience dyspnea, due to the reduced oxygen carrying capacity of hemoglobin (methemoglobin cannot bind oxygen). Levels above 50% can cause seizures, hypotension, coma and death. Sodium nitrite administration for cyanide poisoning at the labeled dosage of 300 mg causes methemoglobinemia, a desirable effect, as methemoglobin binds to cyanide, thus protecting cellular mitochondria. A standard dose of nitrite used for cyanide poisoning is 300 mg up to 600 mg. Note that methemoglobin levels have never risen higher than 3% at the currently used therapeutic doses (<75 mg) in 80 volunteers in phase I studies at the NIH.

The Sponsor of this study protocol, [name], has previously held an IND for sodium nitrite (IND # 70,411) for cardiovascular applications and currently has an approved IND for the use of sodium nitrite for lung transplant recipients (IND # 111,643). The cardiovascular IND involved the administration of sodium nitrite to 69 normal volunteers in 4 phase I-II clinical trials without observed adverse effects. He has also treated 11 participants with sickle cell disease on this IND without observed adverse effects. The lower doses of nitrite used in these investigational treatment regimens – 60-120 mg daily or 20-40% of the dose (300 mg) used in the emergency treatment of cyanide poisoning—do not produce methemoglobin levels greater than 3% and have not been associated with clinically significant hypotension. There have been no adverse events noted in the 80 treated normal human volunteers and patients with sickle cell disease. In another study by [name] et al., 18 healthy adults received an infusion of sodium nitrite totaling 75 mg (15 minutes each x 2 infusions). This was associated with a 7 mm Hg decrease in mean arterial pressure, a peak methemoglobin of less than 3% and no other significant effects. Note this single dose is 1.9 times the larger single dose (tid) we plan to use in this trial.

In [name] current pilot study, 20 mg tid were used, which were lower or similar to the doses of nitrite cited and used safely in any of the noted studies.

To summarize, we anticipate the following symptoms by organ system and likely frequency of risk:

#### Gastrointestinal

- Common: none
- Frequent: none
- Infrequent: dry mouth
- Rare: nausea, abdominal pain and vomiting

#### Hematologic

- Common: none
- Frequent: none
- Rare: methemoglobinemia

#### Cardiovascular

- Common: none
- Frequent: hypotension in older participants on higher nitrite doses
- Rare: flushing, tachycardia, hypotension in healthy controls

#### Neurologic

- Common: none
- Frequent: none
- Rare: headache, dizziness, seizure, coma

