#### Respiratory

- Common: none
- Frequent: none
- Rare: tachypnea, dyspnea, cyanosis

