## 8.2 ADVERSE EVENTS REPORTING TIMELINES

Life-threatening or fatal unexpected adverse events associated with the use of the study drug or procedures must be reported to the DSMB Chair and to the IRB within 24 hours of discovery of the incident with subsequent follow-up submission of a detailed written report.

The FDA will be notified by telephone or facsimile transmission of a human adverse event that is fatal or life-threatening no later than 7 calendar days after receiving the respective human adverse event information, followed by the subsequent submission of a written IND Safety Report.

Serious and unexpected adverse events associated with the use of the study drug or procedures will be reported within 48 hours to the DSMB Chair and the IRB with subsequent follow-up submission of a detailed written report in accordance with the respective policies and procedures of the IRB. Written IND Safety Reports will be submitted to the FDA as soon as possible and, in no event, later than 15 calendar days following the investigator-sponsor's receipt of the respective adverse event information. All AE and SAE will be reported to the DSMB quarterly.

A summary report of the findings will be prepared and submitted to the regulatory agencies as required.

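### High-dose toxicities are listed as anticipated and Section 8 never defines unexpected, so a serious but not life-threatening nitrite event could bypass the 48-hour report to the DSMB Chair and IRB

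*Combined protocol and SAP*

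**What the plan says.** Section 6.1.1 closes its review of nitrite toxicity with a list by organ system, introduced by "To summarize, we anticipate the following symptoms by organ system and likely frequency of risk". Under Neurologic it has "Rare: headache, dizziness, seizure, coma"; under Respiratory, "Rare: tachypnea, dyspnea, cyanosis"; under Hematologic, methemoglobinemia as rare.

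Earlier in 6.1.1, cyanosis, dyspnea and tachypnea appear in case reports attributed to high-dose exposure, by way of methemoglobinemia. Cyanosis is placed at methemoglobin above roughly 30%. Of higher levels the section says "Levels above 50% can cause seizures, hypotension, coma and death". Of investigational regimens of 60 to 120 mg daily it says that they "do not produce methemoglobin levels greater than 3% and have not been associated with clinically significant hypotension".

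On reporting, Section 8 adopts the FDA definitions of AE and SAE and promises an immediate report to the IRB and FDA for SAEs that are unexpected and related. Section 8.1 then gives a study definition of an SAE that itself requires the event to be unexpected. Section 8.2 sets a 24-hour report to the DSMB Chair and IRB for unexpected fatal or life-threatening events. For the rest it says: "Serious and unexpected adverse events associated with the use of the study drug or procedures will be reported within 48 hours". It also sends all AEs and SAEs to the DSMB quarterly.

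**The concern.** The fast reports exist so that people outside the study team can react to a surprising drug effect. Which events count as surprising depends on one word, *unexpected*, that the protocol neither defines nor ties to a reference document. The only list of anticipated drug effects in the documents is the one in Section 6.1.1, so whoever classifies an event is likely to look there. That list includes toxicity which, on the section's own evidence, should not be seen near the trial dose.

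If a drug-related seizure leading to admission, or a symptomatic methemoglobinemia that meets a seriousness criterion, is judged expected because it is listed, it falls outside the 48-hour report. Under Section 8.1 it would not count as a study SAE either. These are events on which prompt independent review of nitrite in people aged 70 or over would be wanted.

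**Working it through.** No sample-size or power figure is involved. The check compares the risk text with the reporting rules.

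**1. Dose.** Sections 2.3.4 and 10 give 20 mg three times daily: 20 × 3 = 60 mg a day. Section 6.1.1 describes 60 to 120 mg daily as 20 to 40% of the 300 mg used for cyanide poisoning; 60/300 = 20% and 120/300 = 40%, so that figure reproduces and the trial sits at the lower end. One sentence in 6.1.1 calls a 75 mg infusion 1.9 times the larger single dose planned, which implies 75/1.9 = 39.5 mg, whereas 75/20 = 3.75. Those passages must be reconciled. The point does not depend on the answer, since 3 × 39.5 = 118 mg a day is still inside the 60 to 120 mg range.

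**2. Distance from the listed toxicity.** The maximum methemoglobin reported at these doses is 3%.
- Cyanosis, about 30%: 3/30 = 0.10, one tenth of the level.
- Seizure and coma, above 50%: 3/50 = 0.06, about one seventeenth of the level.

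Seizure and coma come from the sentence on levels above 50%. They are not among the case-report symptoms; cyanosis is.

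**3. Reporting routes.**

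| Route | Must be unexpected? | Other conditions | Reaches DSMB |
|---|---|---|---|
| Section 8, immediate, IRB and FDA | Yes | SAE, related | Not stated |
| Section 8.2, 24 hours | Yes | Fatal or life-threatening, associated | Chair |
| Section 8.2, 48 hours | Yes | Serious, associated | Chair |
| Sections 8.2 and 10, FDA 7 days | Not in that sentence | Fatal or life-threatening | Yes, by Section 10; no deadline |
| Section 9.2, immediate to an investigator, then IRB per institutional requirements | No | All AEs and SAEs | Not stated |
| Section 8.2, quarterly | No | All AEs and SAEs | Yes |

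**4. Three cases, each drug-related and judged expected.**
- Life-threatening coma: misses the 24-hour report, but the FDA 7-day notice applies and goes to the DSMB.
- Seizure with hospitalization, not life-threatening: misses the 48-hour report. The 7-day notice does not apply. The quarterly listing is the only stated route to the DSMB.
- Cyanosis that is not serious: never within the 24- or 48-hour routes, so nothing is lost.

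The gap is the middle case.

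**5. SAE definition.** Section 8 treats unexpected and related as conditions added to an SAE, and Section 8.2 writes serious and unexpected as two properties. Section 8.1 builds unexpectedness into the SAE itself. These cannot all hold. Under 8.1 the middle case would also drop out of the yearly SAE summary that Section 8 promises to the FDA and IRB.

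**6. Hypotension.** The Cardiovascular list has "Frequent: hypotension in older participants on higher nitrite doses" and also calls hypotension rare in healthy controls, while the text above it reports no clinically significant hypotension at these doses. Section 2.1 enrolls healthy adults aged 70 or over, so a participant is both older and healthy; Section 10 offers nothing below 20 mg tid, and *higher* is not defined. The anticipated frequency for this population cannot be read off.

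**The case against.** The strongest reply is that no sentence makes Section 6.1.1 the reference for expectedness. It is a risk disclosure, and listing a grave but remote effect as rare is cautious. That stands: a reader might infer that a listed seizure *would* count as expected, but the documents support only that it *could*. The concern survives because no other reference is named.

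A reader might also infer that a coma would reach the DSMB only at the quarter. The documents do not support this. As written, the FDA 7-day sentence is not limited to unexpected events, and Section 10 sends that section's reports to the DSMB. The sentence does follow one about unexpected events, and the DSMB copy has no deadline, so the protection is real but loosely drafted.

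Other safeguards do not turn on expectedness: immediate notice to an investigator, IRB reporting under institutional rules and communication to the IND sponsor (9.2), review of safety data as generated (9.4), and the methemoglobin check at interim visits (Section 10). None guarantees prompt notice to the DSMB. The Chair may call an emergency meeting (9.1), but only on something already known to the Chair.

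Two further inferences fail. Hypotension is not unclassifiable for reporting: it is listed either way, and only its frequency is unclear. And the record of no adverse events in 80 treated people concerns any adverse event; it does not settle how a seizure would be classified.

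**Conclusion.** The point holds as a limited gap in safety reporting. For a serious, drug-related event that is not life-threatening and is on the 6.1.1 list, the stated notice to the DSMB Chair could lengthen from 48 hours to as much as one quarter (365/4, about 91 days, against a 12-week intervention of 12 × 7 = 84 days). That interval is an upper limit for this class of event alone.

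The conclusion assumes that the person classifying the event consults the 6.1.1 list, and that no separate reference safety document outside this protocol governs expectedness. The documents give no basis for saying how often such an event would occur, and none is claimed. The conflict over the SAE definition between Sections 8 and 8.1 stands whatever is assumed about the list. This is an inexpensive improvement; it is not evidence that events would go unreported.

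**What to change.** 1. In Section 6.1.1, split the list into effects observed at doses in the trial's range and effects known only from excess exposure or from methemoglobin levels far above those reported at such doses.
2. In Section 8, define unexpected, name the reference used, and state that effects in the second group are unexpected for reporting under Sections 8 to 8.2 and Section 10.
3. Remove the requirement of unexpectedness from the SAE definition in Section 8.1, so that it agrees with Section 8.
4. Reconcile the two hypotension entries with each other, with the statement on hypotension in the 6.1.1 text, and with a single-dose population aged 70 or over.

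The cost is protocol wording and probably a few more expedited reports from about 35 nitrite participants. The first group may be short, because 6.1.1 reports no adverse events in the people treated so far. That should add little burden, since the 24- and 48-hour routes also require a life-threatening or serious event; a non-serious headache would not enter them. Visits, endpoints, sample size and clinical management are unchanged.
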